### **7.17.3 Vital Signs**

Observed and change from baseline vital signs values will be summarized at each timepoint. Vital signs data will be listed by subject at each timepoint.

#### **7.17.4 Electrocardiograms**

Shift tables will be presented that summarize the overall ECG interpretation as normal, abnormal not clinically significant, or abnormal clinically significant from baseline to each post-baseline time point.

Individual ECG data will be listed.

A separate statistical analysis plan will be prepared for the Holter monitoring data following an Early Precision QT (EPQT) analysis. This is not included within this statistical analysis plan.

#### **7.17.5 SARA Assessment**

Scale for the Assessment and Rating of Ataxia (SARA) scores for individual item will be summarized descriptively. Observed and change from baseline in SARA individual and total scores will be summarized at each timepoint.

Total SARA score for each subject will be calculated including score for gait, stance, sitting, speech disturbance and mean score of finger chase, nose-finger test, fast alternating hand movements and heel-shin slide.

#### **7.18 Planned Interim Analysis**

There is no formal interim analysis planned.

However, ongoing assessments of the PK, safety and tolerability, will be performed for dose escalation meetings.

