3. STUDY DESIGN

3.1. Overview of Study Design

In this randomized, double-blind, placebo-controlled Phase 1 study, a single ascending dose of RGLS8429 or placebo will be administered via SC injection to healthy volunteers to evaluate the safety, tolerability, and PK of RGLS8429. Eight subjects will be randomized 3:1 to receive RGLS8429 or placebo in each cohort.

Cohort 1	0.5 mg/kg RGLS8429 or placebo
Cohort 2	1.0 mg/kg RGLS8429 or placebo
Cohort 3	2.0 mg/kg RGLS8429 or placebo
Cohort 4	4.0 mg/kg RGLS8429 or placebo

In each cohort, 6 subjects will be randomized to receive RGLS8429 and 2 will be randomized to receive placebo. Enrollment into subsequent cohorts will be initiated after review of safety (AEs and safety laboratory tests) from the prior cohort.

For Cohort 1, the first two subjects will receive RGLS8429 or placebo (randomized such that one subject receives RGLS8429 and one receives placebo) and this sentinel group will be monitored for 48 hr prior to dosing the remaining subjects in the cohort.

An unblinded pharmacist will be responsible for preparing RGLS8429 or placebo and providing the study drug to blinded study personnel for administration according to the randomization procedures.

Subjects will be admitted to the study center on Day -1, one day prior to the day of study drug administration (Day 1), and will be discharged on Day 2, no less than 6 hr after the collection of the 24-hr PK sample. Subjects will be followed for a total of 4 weeks after dosing and will return to the site for follow-up visits weekly from Weeks 1 through 4. The sentinel subjects will remain in the clinic for 48 hr after dosing.

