3.2. Dose Escalation and Stopping Rules

Prior to dose escalation, the Sponsor and the Investigator will perform a blinded review of the safety data (e.g., AE and safety laboratory tests through Day 15) on all subjects at the current dose level to make a dose escalation decision.

If 2 or more subjects at the same dose level experience the same or similar Grade ≥ 2 AEs (including clinically significant laboratory AEs) or if 1 subject experiences a Grade ≥ 3 AE or a SAE judged to be related to study drug, the Sponsor's Lead Physician will be unblinded to the treatment. Also, if 2 subjects develop stage 1 AKI or 1 subject develops stage 2 AKI the Sponsor's Lead Physician will be unblinded to the treatment.

The Sponsor's Lead Physician will determine whether the nature, severity, or number of event(s) warrants:

1. Continuing with the study as planned
2. Continuing with the study, but add additional safety evaluation(s)
3. Suspend dose escalation and enroll additional subjects at the same dose level
4. Add an intermediate-dose cohort or adjust the next dose level
5. Suspend or terminate the study

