8.4.4. Pharmacokinetic Analysis

PK samples will be analyzed using a validated, sensitive, specific method. The laboratory analyzing the PK samples will be unblinded to ensure that PK analysis is performed only on subjects receiving RGLS8429. Placebo samples will be analyzed if necessary. Descriptive statistics for plasma concentrations by time point and by cohort will be tabulated. Descriptive statistics for PK parameters will be summarized by cohort.

Concentration data will be presented and summarized for the PK Full population.

Using non-compartmental methods, the plasma and urine concentration data will be used to derive the following PK parameters: C_{max} , T_{max} , AUC_{0-24} , AUC_{0-t} , AUC_{inf} (where calculable), $t_{1/2}$, CL/F , V_z/F , fe , and Ae . Additional PK parameters may be calculated as appropriate. The PK Evaluable Population will be used for these analyses.

Dose proportionality will be explored using the power model for C_{max} , AUC_{0-24} , AUC_{0-t} , and AUC_{inf} as data permit.

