### **3.3 Randomization and Treatment Assignments**

This study will be double-blind and placebo-controlled. There will be 4 SAD cohorts. Eight subjects will be enrolled into each of the 4 dosing cohorts. Subjects in each cohort will be randomized at a ratio of 3:1 to receive RGLS8429 or placebo. In each cohort, 6 subjects will be randomized to receive RGLS8429 and 2 will be randomized to receive placebo.

ICON will provide a randomization schedule and eligible subjects will be randomized sequentially to receive the study drug assigned to the corresponding randomization number. Subjects may be randomized once all Screening and Day -1 procedures have been completed and eligibility has been confirmed by the Investigator. Details regarding randomization procedures will be provided in the study reference manual.

Enrollment into subsequent cohorts will be initiated after review of safety (AEs and safety laboratory tests) from the prior cohort. The investigator or a designee will assign sequential subject identification numbers to the subjects as they are screened and enrolled in the study.

An unblinded pharmacist will be responsible for preparing RGLS8429 or placebo and providing the study drug to blinded study personnel for administration according to the Pharmacy instructions within the Study Reference Manual.

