#### **4 CHANGES IN THE CONDUCT OF THE STUDY OR PLANNED ANALYSIS**

All analyses specified in this SAP are consistent with the final study protocol (Version 3.0, dated 06 June 2022). Any changes in the analyses provided or any additional analyses performed will be documented in the clinical study report (CSR).

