| RGLS8429
0.5 mg/kg
(N=xx) | RGLS8429
1.0 mg/kg
(N=xx) | RGLS8429
2.0 mg/kg
(N=xx) | RGLS8429
4.0 mg/kg
(N=xx) | Pooled
RGLS8429
(N=xx) | Pooled
Placebo
(N=xx) |
|---------------------------------|---------------------------------|---------------------------------|---------------------------------|------------------------------|-----------------------------|
|---------------------------------|---------------------------------|---------------------------------|---------------------------------|------------------------------|-----------------------------|

- For PK tables placebo will not be presented

The listing layouts are given below:

| Cohort/ Treatment             | Subject Number/ Age/ Sex/
Race | xxxx | xxxx | xxxx |
|-------------------------------|-----------------------------------|------|------|------|
| Cohort 1/ RGLS8429 0.5 mg/kg  | XXXX-XXXX/ xx/ X/ X               |      |      |      |
| Cohort 1/ Placebo             | XXXX-XXXX/ xx/ X/ X               |      |      |      |
| Cohort 2/ RGLS8429 1.00 mg/kg | XXXX-XXXX/ xx/ X/ X               |      |      |      |
| Cohort 2/ Placebo             | XXXX-XXXX/ xx/ X/ X               |      |      |      |
| .....                         |                                   |      |      |      |

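### Does naming PK for the dose-escalation meetings in SAP 7.18 undermine the blinded safety review in Protocol 3.2?

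*SAP*

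**What the plan says.** SAP 7.18 plans no formal interim analysis, but adds that "ongoing assessments of the PK, safety and tolerability, will be performed for dose escalation meetings".

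Protocol 3.2 sets the escalation decision: "the Sponsor and the Investigator will perform a blinded review of the safety data (e.g., AE and safety laboratory tests through Day 15"). This covers everyone dosed at that level. It opens one route to unblinding, for the Sponsor's Lead Physician alone, after a specified adverse-event or kidney-injury trigger.

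SAP 3.3 gives the between-cohort step as "Enrollment into subsequent cohorts will be initiated after review of safety (AEs and safety laboratory tests) from the prior cohort". Protocol 3.1 and SAP 3.1 say the same.

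On the assay, Protocol 8.4.4 states: "The laboratory analyzing the PK samples will be unblinded to ensure that PK analysis is performed only on subjects receiving RGLS8429". Placebo samples are run only if needed. Under SAP 7.8.4 the PK Full Population contains RGLS8429 recipients only.

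Neither document says who prepares PK for an escalation meeting, who receives it, or whether it is shown by subject or in aggregate.

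**The concern.** Two things look wrong.

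First, the documents differ on what informs escalation. SAP 7.18 names PK; every other description of the review names safety alone. SAP Section 4 nevertheless declares that "All analyses specified in this SAP are consistent with the final study protocol".

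Second, PK in this trial can carry the treatment code. If only active samples are assayed, a subject who appears in a PK listing received RGLS8429 and a subject who does not received placebo. Assaying the placebo samples would not help, because they would be expected to read below quantitation.

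The Investigator takes part in the escalation review, grades adverse events and judges their causality (Protocol 9.2.2 and 9.2.3). SARA is also rated by an Investigator (Protocol 2.3.11). Adverse events and SARA belong to the primary endpoint. If the Investigator learned the allocation around Day 15, those judgements at Day 22 and Day 29 would no longer be blinded.

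**Working it through.** No stated figure is in dispute, so the check compares the texts and then counts what could be exposed.

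**1. Do the texts conflict?**
- Protocol 3.2 requires the review to be blinded. Its list of data is introduced as examples, so PK is not expressly excluded, although the examples are of safety data.
- SAP 3.3 names adverse events and safety laboratory tests, without an open list.
- SAP 7.18 says PK is assessed for the meetings. It does not make PK a criterion for escalation, send it to the Investigator, or call for subject-level display.

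The scope differs, most plainly between SAP 3.3 and SAP 7.18. But nothing in SAP 7.18 lifts the blinding condition. Read together, any PK used at the meeting has to be in a form that keeps the reviewers blinded.

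**2. What would identifiable PK reveal?**
Inputs: 8 subjects per cohort, 6 active and 2 placebo (Protocol 3.1). The Cohort 1 sentinel pair is "randomized such that one subject receives RGLS8429 and one receives placebo".
- Cohort 1: the other six subjects hold 6 − 1 = 5 active and 2 − 1 = 1 placebo. Possible allocations = 2 × 6 = 12, so a guess at the whole cohort is right with probability 1/12 = 8.3%.
- Cohorts 2 and 3: C(8,2) = 28 each, so 1/28 = 3.6%.
- A by-subject listing reduces each count to 1.
- A cohort summary on n = 6 without identifiers reveals nothing new, because the 6:2 split is already known.

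**3. How many subjects could be affected?**
Four cohorts give three escalation decisions (1 to 2, 2 to 3, 3 to 4).

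| PK display | Subjects exposed | Placebo subjects exposed |
|---|---|---|
| Cohort summaries, or individual data that cannot be linked to a subject | 0 of 32 | 0 of 8 |
| Identifiable, at one meeting | 8 of 32 | 2 of 8 |
| Identifiable, at all three meetings | 3 × 8 = 24 of 32 | 3 × 2 = 6 of 8 |

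Recoding alone does not guarantee the first row. Dosing is by weight and exact sampling times go into the CRF (Protocol 2.3.12), so a recoded profile that shows the dose in mg or the actual times could be traced back to a subject.

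**4. What remains to be assessed after Day 15?**
- Weekly visits: Days 22 and 29, so at most 2 of 4, over 29 − 15 = 14 days.
- Post-dose SARA (4–6 hr, Day 2, Day 29): 1 of 3.
- Holter: none. Recording stops on Day 2, and the central reader is blinded (Protocol 2.3.6).

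These are upper limits. Neither document gives a meeting date or an assay turnaround, so fewer visits may remain.

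**5. Do SAP Sections 4 and 8 add to the problem?**
Little. Section 4 speaks of analyses that the SAP specifies, and the SAP specifies no table, listing or parameter for an escalation meeting. Section 8 notes that "For PK tables placebo will not be presented", but its layouts serve the clinical study report (SAP Section 1), from data retrieved after database lock (SAP Section 5). They do not show what a blinded meeting would see.

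**The case for a change.** The strongest case for a change is that the safeguard is only implied. The documents spell out blinding for the pharmacist, the pharmacy staff and clinical research associate, the PK laboratory, the Holter reader and the Sponsor's Lead Physician, yet say nothing about PK prepared for escalation. SAP 6.1.1 has the pharmacokineticist discuss excluded concentrations with the sponsor and gives no blinding status for that exchange. The open list in Protocol 3.2 gives examples of safety data, which PK is not, and SAP 3.3 has no open list at all. A sentence or two would settle it.

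Much of this stands. The mismatch in scope is genuine, the counts are right, and by-subject PK would break the blind in the cohort under review. What does not stand is the step from silence to a faulty plan. The Protocol states the governing rule, that the review is blinded, and the SAP does not set it aside. The laboratory is unblinded, so the treatment code need not pass through the blinded team for PK to be produced. Operational detail is left elsewhere to the Study Reference Manual and the Laboratory Manual. Those are not available here, so they cannot be credited with covering the point; equally, silence in these two documents does not show that no rule exists.

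**Conclusion.** The concern identifies a real difference in wording but does not call for a change. A team that follows the plan as written must keep the escalation review blinded, and can do so by bringing PK only as cohort summaries or in a form that cannot be linked to subjects. Exposure is then 0 of 32.

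The upper figure of 24 of 32 subjects (6 of 8 placebo) needs identifiable by-subject PK at all three meetings, which no document plans and Protocol 3.2 rules out. It also assumes no replaced subjects, no added cohorts and no placebo samples assayed. Even then, the allocation counts measure identifiability, not bias. The judgements open to influence would be the Investigator's ratings at no more than two late visits, and only if the Investigator, and not just the Sponsor, saw the data. Safety is summarised descriptively without formal tests (Protocol 8.4.3, SAP 7.3), so no test or error rate is at stake.

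Confidence is high that the texts differ. That any blinding consequence would follow is conditional and unlikely under the stated rules.

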## 8 GENERAL CONVENTIONS FOR TABLES, LISTINGS, AND FIGURES

Tables and listings will be presented in landscape mode with minimum of 3/4" bound edge margin and 3/8" other margins on 8.5" x 11" paper.

Times new roman font size of no less than 8 point will be used for tables and listings.

A source line will be included on the bottom of each page of all tables and listings. It will contain the SAS code program name and the run date and time.

Each variable is recorded to a specific number of decimal places. If the raw data is presented with varying precision, then the least precise value will be considered as the data precision.

For summary tables, unless otherwise specified, the number of decimal places provided in the tables and listings will be based on the accuracy of the least accurate value in the raw data as follows:

|                       |                                                                      |
|-----------------------|----------------------------------------------------------------------|
| n                     | Integer                                                              |
| Arithmetic mean       | 1 decimal place more than the least accurate number in the raw data  |
| SD                    | 2 decimal places more than the least accurate number in the raw data |
| %CV                   | 2 decimal places                                                     |
| Geometric mean        | 1 decimal place more than the least accurate number in the raw data  |
| Geometric CV          | 2 decimal places                                                     |
| Median                | 1 decimal place more than the least accurate number in the raw data  |
| Quartiles (Q1 and Q3) | 1 decimal place more than the least accurate number in the raw data  |
| Minimum               | same number of decimal places as raw data                            |
| Maximum               | same number of decimal places as raw data                            |
| Confidence interval   | same number of decimals as the associated statistic                  |
| Percentage            | 1 decimal place                                                      |
| Geometric mean ratio  | 2 decimal places                                                     |

The sample column layouts are given below:

| RGLS8429
0.5 mg/kg
(N=xx) | RGLS8429
1.0 mg/kg
(N=xx) | RGLS8429
2.0 mg/kg
(N=xx) | RGLS8429
4.0 mg/kg
(N=xx) | Pooled
RGLS8429
(N=xx) | Pooled
Placebo
(N=xx) |
|---------------------------------|---------------------------------|---------------------------------|---------------------------------|------------------------------|-----------------------------|
|---------------------------------|---------------------------------|---------------------------------|---------------------------------|------------------------------|-----------------------------|

- For PK tables placebo will not be presented

The listing layouts are given below:

| Cohort/ Treatment             | Subject Number/ Age/ Sex/
Race | xxxx | xxxx | xxxx |
|-------------------------------|-----------------------------------|------|------|------|
| Cohort 1/ RGLS8429 0.5 mg/kg  | XXXX-XXXX/ xx/ X/ X               |      |      |      |
| Cohort 1/ Placebo             | XXXX-XXXX/ xx/ X/ X               |      |      |      |
| Cohort 2/ RGLS8429 1.00 mg/kg | XXXX-XXXX/ xx/ X/ X               |      |      |      |
| Cohort 2/ Placebo             | XXXX-XXXX/ xx/ X/ X               |      |      |      |
| .....                         |                                   |      |      |      |

## 9 LIST OF TABLES, FIGURES, AND LISTINGS

| Table/Figure Number   | Table/Figure Name                                                                                                                                                                                                                  |
|-----------------------|------------------------------------------------------------------------------------------------------------------------------------------------------------------------------------------------------------------------------------|
| Section 14.1   | Demographic and Subject Characteristics Data Summaries                                                                                                                                                                      |
| Table 14.1.1          | Summary of Subject Disposition (Screened Population)                                                                                                                                                                               |
| Table 14.1.2          | Analysis Populations                                                                                                                                                                                                               |
| Table 14.1.3          | Demographic and Baseline Characteristics (Randomized Population)                                                                                                                                                                   |
| Table 14.1.4          | Medical and Surgical History Summary (Randomized Population)                                                                                                                                                                       |
| Section 14.2   | Pharmacokinetic/Biomarker Data Summaries                                                                                                                                                                                    |
| Section 14.2.1 | Pharmacokinetic Data Summaries                                                                                                                                                                                              |
| Table 14.2.1.1        | Summary of RGLS8429 Plasma Concentrations (units) by Timepoint (PK Full Population)                                                                                                                                                |
| Table 14.2.1.2        | Summary of RGLS8429 Plasma PK Parameters (PK Evaluable Population)                                                                                                                                                                 |
| Table 14.2.1.3        | Summary of RGLS8429 Plasma PK Parameters after excluding Outliers (PK Evaluable Population)
Note: Outliers are included (e.g., estimates of T1/2 if a time span of at least 2 half-lives is not used or $r^2_{adj} \leq 0.80$ ) |
| Table 14.2.1.4        | Summary of RGLS8429 Urine PK Parameters (PK Evaluable Population)                                                                                                                                                                  |
| Table 14.2.1.5        | Statistical Analysis of Dose Proportionality of Pharmacokinetic Parameters (PK Evaluable Population)                                                                                                                               |
| Figure 14.2.1.1       | Mean (+/-SD) of Plasma Concentration of RGLS8429 -Time Profiles by Treatment Group (PK Full Population)
Note: Present both linear and semi-log                                                                                  |
| Figure 14.2.1.2       | Plot of RGLS8429 Dose-Proportionality Regression (PK Evaluable Population)                                                                                                                                                         |
| Section 14.2.2 | Biomarker Data Summaries                                                                                                                                                                                                    |
| Table 14.2.2.1        | Summary Statistics of Urine Biomarker Variables (Biomarker (PD) Population)                                                                                                                                                        |
| Section 14.3   | Safety Data Summaries                                                                                                                                                                                                       |
| Section 14.3.1 | Displays of Adverse Events                                                                                                                                                                                                  |
| Table 14.3.1.1        | Overall Summary of Treatment-Emergent Adverse Events (Safety Population)                                                                                                                                                           |
| Table 14.3.1.2        | Summary of Treatment-Emergent Adverse Events by System Organ Class and Preferred Term (Safety Population)                                                                                                                          |
| Table 14.3.1.3        | Summary of Treatment-Emergent Adverse Events by Maximum Severity Grade (Safety Population)                                                                                                                                         |
| Table 14.3.1.4        | Summary of Treatment-Emergent Adverse Events Related to Study Drug (Safety Population)                                                                                                                                             |
| Table 14.3.1.5        | Summary of Treatment-Emergent Serious Adverse Events (Safety Population)                                                                                                                                                           |

|                       |                                                                                                                                               |
|-----------------------|-----------------------------------------------------------------------------------------------------------------------------------------------|
| Table 14.3.1.6        | Summary of Incidence of Dose-Limiting Toxicity (Safety Population)                                                                            |
| Table 14.3.1.7        | Concomitant Medication Summary (Safety Population)                                                                                            |
| Section 14.3.2 | Listings of Deaths, Other Serious and Certain Significant Adverse Events                                                               |
| Table 14.3.2.1        | Listing of Deaths (Safety Population)                                                                                                         |
| Table 14.3.2.2        | Listing of Serious Adverse Events (Safety Population)                                                                                         |
| Table 14.3.2.3        | Listing of Adverse Events Resulting in Discontinuation of Study (Safety Population)                                                           |
| Section 14.3.4 | Abnormal Laboratory Value Listing                                                                                                      |
| Table 14.3.4          | Listing of Abnormal Laboratory Results (Safety Population)                                                                                    |
| Section 14.3.5 | Additional Safety Data Summaries                                                                                                       |
| Table 14.3.5.1        | Summary Statistics of Absolute and Change from Baseline for Clinical Laboratory Parameters (Safety Population)
Note: continuous tests only |
| Table 14.3.5.2        | Shift Table for Clinical Laboratory Parameters (Safety Population)                                                                            |
| Table 14.3.5.3        | Summary Statistics of Absolute and Change from Baseline for Vital Signs (Safety Population)                                                   |
| Table 14.3.5.4        | Shift Table for Electrocardiogram Interpretations (Safety Population)                                                                         |
| Table 14.3.5.5        | Summary Statistics of Absolute and Change from Baseline in Scale for the Assessment and Rating of Ataxia (SARA) (Safety Population)           |

